function, in patients with PMI and thereby, patients will be treated more appropriately and major complications could (hopefully) be prevented.

Nowadays, the Revised Cardiac Risk index (RCRI) is commonly used as a predictive tool to estimate the probability of MACE or mortality¹³. The RCRI includes six predictors, which are high risk surgery, history of myocardial infarction (MI), history of cerebrovascular disease, chronic heart failure, elevated creatinine and insulin dependent diabetes. Ford et al. performed a review on the performance of the RCRI in several validation studies and found that this cardiac index only moderately predicts, does not predict events in vascular surgery, and has not been prospectively validated using troponin or other biomarkers to predict MI or other cardiac events¹⁴. Since this publication, several studies reported the added predictive value to the RCRI of one (or more) biomarker(s), including (high sensitive) troponin¹⁵⁻¹⁷, (NT-pro)BNP^{15,16,18-20}, eGFR^{21,22}, CRP^{18,20}, ECG^{23,24} and transthoracic echocardiography^{19,25}. Addition of (high sensitive) troponin, (NT-pro)BNP and/or CRP to the RCRI seems promising for the prediction of MACE as the predictive performance significantly improves compared to the RCRI by itself. To our knowledge, different combinations of several biomarkers together in addition to the RCRI have not been reported yet.

Our primary objective is to investigate and compare the independent prognostic effect of the different PMI phenotypes (myocardial infarction and NITE) and noncardiac MAPE on disability. We will be diagnosing the differing PMI phenotypes using clinical evaluation and biomarkers. The primary endpoint is disability. Disability is assessed using the World Health Organization Disability Assessment Score 2.0 (WHODAS 2.0)²⁶. Our primary hypothesis is that any postoperative troponin elevation regardless of its association with MACE or noncardiac MAPE is independently associated with an increased risk of death and disability.

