2. OBJECTIVES

2.1 Primary objective

To investigate and compare the independent prognostic effect of the different PMI phenotypes (myocardial infarction and NITE) and noncardiac MAPE on disability in patients undergoing elective noncardiac surgery.

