Hospital admittance and intraoperative data collection

For patients who agreed on study participation during the telephone call one week before surgery, informed consent will be signed by the patient and study investigator. If a patient decides to decline study participation at this point, this patient will receive routine care as usual. The treating anesthesiologist will be informed about participation and 7 cc blood will be drawn at the operation theatre immediately before induction of anesthesia. Blood will be collected, processed and stored at the Centrale Biobank (CBB) with corresponding study number. Blood biomarkers will be considered preoperative baseline values. During surgery, the following data will be collected:

- Vital signs, i.e. blood pressure, heart rate and ET-CO₂.
- Blood loss and number of blood transfusions
- Duration of surgery

Collection of intraoperative data is part of routine clinical care; no study related procedures will be conducted.

Postoperative in hospital stay

At postoperative day 1-3, the following procedures will be performed:

- Extra blood (7 cc each time) will be drawn during the standard blood sampling rounds in the morning. Blood will be processed and stored at the CBB.
- At postoperative day 2, an ECG and TTE will be performed by certified study personnel and uploaded at the local electronic health record (EHR) and a digital databank.
- In-hospital MAPE, such as MACE, unplanned ICU admission, respiratory disorders, renal failure, sepsis and/or SIRS and mortality will be monitored.

At the UMCU, troponin-I is routinely monitored in all patients, aged ≥ 60 years, undergoing major noncardiac surgery. In case troponin-I is elevated, routine (i.e. non-study related) hospital protocol procedures involve an ECG and consultation by an anesthesiologist. The anesthesiologist could consult a cardiologist for further examination. Additional diagnostic tests or initiation of therapy is

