7.2 Primary study parameter(s)

The primary outcome, postoperative WHODAS 2.0 after 6 months, will be compared among patients with and without PMI, using Student's t-test or a nonparametric Mann Whitney U test. In case of normality, the mean 6-months WHODAS 2.0 will be calculated together with the accompanying 95% confidence intervals. Otherwise, the median WHODAS 2.0 with interquartile range will be reported.

With respect to the association between the different phenotypes of PMI (i.e. myocardial infarction, NITE and MAPE) and disability, the preoperative, postoperative and the change (meaning difference between pre- and postoperative measurements) in biomarkers are of particular interest. The biomarkers will be analyzed both as continuous variables and using predefined clinical thresholds to define when the each of the biomarkers are elevated.

Combination(s) of different biomarkers and the biomarker by itself in association with postoperative WHODAS 2.0 will be performed. These combination(s) of biomarkers will be related to one of the different phenotypes of PMI. Multivariable linear regression analyses will be performed to adjust for potential confounders including age, gender, comorbidities (cardiovascular risk factors), preoperative WHODAS 2.0 score, RCRI and surgical specialty.

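### The named covariates omit the pre-induction blood biomarkers, so the independent effects of MI, NITE and noncardiac MAPE may keep residual confounding that the collected data could reduce

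*Combined protocol and SAP*

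**What the plan says.** Section 2.1 sets the aim: "To investigate and compare the independent prognostic effect of the different PMI phenotypes (myocardial infarction and NITE) and noncardiac MAPE on disability".

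Section 7.2 plans multivariable linear regression adjusted for "potential confounders including age, gender, comorbidities (cardiovascular risk factors), preoperative WHODAS 2.0 score, RCRI and surgical specialty". Section 7.3 says that the logistic models for disability free survival take similar covariates.

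The biomarkers have a different role in section 7.2. For the association between phenotypes and disability, "the preoperative, postoperative and the change (meaning difference between pre- and postoperative measurements) in biomarkers are of particular interest", and "Combination(s) of different biomarkers and the biomarker by itself in association with postoperative WHODAS 2.0 will be performed". They are exposures there. No biomarker is named as a covariate for a phenotype effect.

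Three other places bear on this:

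- Section 1, on the RCRI: "Addition of (high sensitive) troponin, (NT-pro)BNP and/or CRP to the RCRI seems promising for the prediction of MACE". The same section calls the RCRI's own prediction only moderate.
- Section 1, on PMI: cardiac troponin I above the 99th percentile, with a 10% variation. No rise from the patient's own preoperative value is stated.
- Section 5.3: "7 cc blood will be drawn at the operation theatre immediately before induction of anesthesia", and "Blood biomarkers will be considered preoperative baseline values".

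**The concern.** A patient who comes to surgery with raised troponin or BNP, low hemoglobin or impaired renal function is more likely to cross a postoperative troponin threshold or have a noncardiac event. That patient is also plausibly more disabled, or dead, at six months whatever happens after surgery. Diagnoses recorded as present or absent, and an index with a yes/no creatinine item, capture this only coarsely. CRP has no direct counterpart in the list.

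The PMI definition sharpens the issue. With no rise required, a chronically raised troponin could be counted as postoperative injury, so preoperative troponin is the most direct of the missing covariates.

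The pre-induction sample precedes every exposure, so adjusting for it cannot remove part of an effect that runs through the exposure. What is at stake is how much of the reported phenotype effect is pre-existing risk.

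**Working it through.** **Covariates and baseline information side by side**

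| Baseline state | Carried in 7.2 by | Collected before induction, not named as covariate |
|---|---|---|
| Cardiac | Cardiovascular comorbidities; RCRI items for MI history and heart failure | hsTroponin, BNP |
| Renal | RCRI elevated creatinine (yes/no); chronic renal failure, if counted among the comorbidities | creatinine as a continuous value |
| Inflammation | nothing direct | CRP |
| Anemia | nothing direct | hemoglobin |

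The study's transthoracic echo is done on postoperative day 2, so it is not a baseline covariate and is left out.

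**Inputs**

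- From section 4.4: PMI incidence 11%; pooled target 1,000; dropout 20%; pilot WHODAS means 29% and 15%, an unadjusted difference of 14 points. Analysed: 1,000 x 0.8 = 800, of whom 800 x 0.11 = 88 have PMI and 712 do not.
- Assumed, because the documents give neither: an odds ratio of 1.5 to 2.5 for PMI per SD of a baseline biomarker score, and a slope of 2 to 4 WHODAS points per SD. Both must be read as conditional on the covariates already listed. Marginal values would overstate the bias.

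**Formula**

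Bias in the PMI coefficient = (biomarker difference between PMI and no PMI, in SD) x (WHODAS points per SD).

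For a standard normal score and a logistic model with 11% PMI, the differences are 0.40, 0.66 and 0.84 SD at odds ratios 1.5, 2.0 and 2.5.

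| Odds ratio per SD | Difference (SD) | Bias at 2 points | Bias at 3 points | Bias at 4 points |
|---|---|---|---|---|
| 1.5 | 0.40 | 0.8 | 1.2 | 1.6 |
| 2.0 | 0.66 | 1.3 | 2.0 | 2.6 |
| 2.5 | 0.84 | 1.7 | 2.5 | 3.4 |

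For scale, 0.8/14 = 6% and 3.4/14 = 24%. The 14 points are unadjusted, so these percentages only give an order of magnitude.

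**Wider range**

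With differences of 0.2 to 0.8 SD and slopes of 1 to 5 points, the bias runs from 0.2 x 1 = 0.2 to 0.8 x 5 = 4.0 points.

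**Does a yes/no risk item do the job?**

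A simulation with 2,000,000 patients used a true PMI effect of 7 points, 11% PMI, odds ratios 1.5 to 2.5, slopes 1 to 5, and a risk flag set at the top 10% or 20% of the biomarker. Adjusting for the flag alone gave 7.1 to 9.2 points. Adding the continuous biomarker gave 6.9 to 7.0. A flag removes part of the bias and leaves part.

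The plan's sample size figure plays no part in this check.

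**The case against.** The strongest case against has six parts.

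- **Cardiac and renal state is adjusted for.** This stands. Cardiovascular comorbidities, the RCRI and preoperative WHODAS are all in the list. A reader might infer that baseline risk is uncontrolled; the documents show only that control is imperfect.
- **The list is open, since it gives examples.** True, but that leaves the choice of covariates until after the data are seen.
- **No phenotype regression is written out in 7.2, and preoperative biomarkers already enter as exposures.** Both are true. But the objective needs a model with the phenotypes as exposures. Estimating a biomarker's own association with WHODAS does not adjust a phenotype coefficient.
- **Section 1 speaks of predicting major adverse cardiovascular events (MACE), not disability.** This stands. MI is a MACE component, so the text supports the link from biomarker to exposure. The link to six-month disability, given preoperative WHODAS and comorbidities, is plausible but assumed.
- **Availability is documented for Utrecht only.** This stands. A reader might infer that all 1,000 pooled patients have the sample. Section 4.4 says of Toronto only that it runs a similar study with the same eligibility criteria. Section 5.3 also plans the assays as one batch after the last discharge, so the values do not exist yet.
- **Adjusting for preoperative troponin changes the question.** This partly stands. It moves the PMI estimate toward acute injury, which is one reading of independent effect but not the only one.

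**Conclusion.** The point holds as a gap in the stated adjustment. Baseline values that the protocol collects, and partly describes as informative beyond the RCRI, have no stated place as covariates in the analysis of phenotype effects. Residual confounding is plausible and could be reduced at little cost.

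Its size is unknown. The 0.8 to 3.4 points rest wholly on assumed odds ratios and slopes, and they illustrate the PMI coefficient only; nothing was calculated for noncardiac MAPE or for MI against NITE.

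A reader might go further and infer a seriously inflated false-positive rate. With an assumed residual SD of 18 to 25, the standard error is SD x sqrt(1/88 + 1/712) = 2.03 to 2.82, and the nominal 5% becomes 6% to 38% over the grid above. That width mainly reflects the assumptions. The documents give no SD, odds ratio or slope to narrow it, so it should not be quoted as a property of the plan.

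**What to change.** Write out the models in which MI, NITE or noncardiac MAPE is the exposure: the 7.2 linear model for WHODAS and the 7.3 logistic model for disability free survival. For each, prespecify two versions and report them side by side:

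1. The covariates already listed.
2. The same plus pre-induction log hsTroponin, log BNP, log CRP, hemoglobin, and creatinine or eGFR, all continuous.

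Fit the second version in the Utrecht data. Fit it in the pooled data only if Toronto has comparable baseline samples, and say so in the SAP.

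**Cost:** SAP wording and up to five more terms. At Utrecht alone, 500 x 0.8 = 400 patients would be analysed, about 400 x 0.11 = 44 with PMI. The linear model can carry the terms, though with less precision than the pooled data. The number of terms in the logistic model should be checked against the number of patients in the smaller outcome group. At Utrecht no new visit, sample or assay is needed. The second version shifts the PMI estimate toward acute injury, which is why both should be shown.

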5. METHODS

5.1 Study parameters/endpoints

5.1.1 Main study parameter/endpoint

Disability is expressed by the WHODAS 2.0, which is based on difficulties experienced by the respondent in different functional domains including, cognition, mobility, self-care, getting along, life activities and participation during the previous 30 days. Disability is defined as a decrement in each functioning domain corresponding to score between 0% and 100%, in which no disability stands for a score of 0% and full disability represents a score of 100%, including death. The WHODAS 2.0 is easy to use and patient centered (see F1 for the questionnaire). In a validation study including noncardiac surgical patients, the WHODAS 2.0 has been found to be a clinically acceptable, valid, reliable and responsive instrument for measuring postoperative disability²⁷.

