5.1.2 Secondary study parameters/endpoints

- *Disability free survival* is defined as being alive with a WHODAS score $\leq 25\%$ and no increase of the pre-operative score $\geq 25\%$ at 6 months after surgery.
- *An in-hospital major adverse postoperative events (MAPE)*, which could be distinguished in:
 - o *Major adverse cardiovascular event (MACE)*, which is defined as the composite endpoint of:
 - Cardiovascular death, defined as death resulting from an acute myocardial infarction, sudden cardiac death, death due to heart failure, death due to stroke, and any acute death unconfirmed yet probably due to a cardiovascular cause.
 - Non-fatal myocardial infarction, defined in accordance to the third universal definition of myocardial infarction¹⁰.
 - Non-fatal cardiac arrest.
 - Non-fatal ventricular fibrillation.
 - Ventricular arrhythmia with hemodynamic compromise.
 - Atrial fibrillation requiring cardioversion.
 - Pulmonary embolism, defined as a new thrombus within the pulmonary arterial system confirmed on CTA
 - Stroke confirmed on CT.
 - o *Noncardiac MAPE*, which is a composite outcome consisting of:
 - Respiratory failure including pneumonia and hypoxia or hypercapnia leading to ICU admission for respiratory support

- Sepsis and/or systemic inflammatory response syndrome (SIRS), defined as life-threatening organ dysfunction caused by a dysregulated host response to infection²⁸.
- Renal failure, defined as AKIN criteria or renal replacement therapy.
- Unplanned ICU admission
- Unplanned medium care admission
- Reoperation
- *Length of hospital stay, defined as the number of days from the end of surgery until day of discharge*
- *In-hospital all-cause mortality*
- *6-month all-cause mortality*
- *6-month MACE*

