5.1.3 Other study parameters

- Baseline characteristics including:
 - Demographics, i.e. age, gender, BMI, smoking status, American Society of Anesthesiologists class (ASA).
 - Comorbidities, including history of the following diseases: myocardial infarction, cerebrovascular disease, congestive heart failure and cancer. Currently diagnosed with: diabetes, coronary artery disease, chronic renal failure, cancer, chronic obstructive pulmonary disease, peripheral vascular disease, and hypertension.
 - Medication use, including beta blockers, angiotensin converting enzyme inhibitors, calcium blockers, diuretics, statins, insulin, oral antidiabetics.
 - Surgical history, including coronary revascularization, pacemaker or implantable cardioverter defibrillator (ICD).
 - Laboratory results of preoperatively measured blood biomarkers, i.e. hsTroponin, C-reactive protein (CRP), brain natriuretic peptide (BNP), hemoglobin (Hb) and creatinine in blood. Imaging biomarkers are electrocardiogram (ECG) and transthoracic echocardiogram (TTE).
 - Referral of the screening anesthesiologist at the preanesthesia consultation clinic to a cardiologist or other specialist before surgery
 - Preoperative WHODAS 2.0
- Intraoperative:
 - Anesthesia related including type of anesthesia (general or spinal), vital signs (i.e. blood pressure, heart rate, eCO2).

- Surgical related factors: surgical risk, surgical specialty, blood loss, number of blood transfusions and fluid balance.
- Postoperative:
 - Troponin I monitoring at postoperative day 1-3 as being part of routine care.
 - Laboratory results of postoperative measured blood biomarkers, i.e. hsTroponin, CRP, BNP, Hb and creatinine in blood on postoperative day 1-3. Imaging biomarkers (ECG and TTE) on postoperative day 2.
 - Rehospitalization within 6 months after surgery.

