- The added prognostic value of each of the biomarkers (or combinations of biomarkers) will be tested to predict MACE, both in-hospital and at 6-months. The biomarkers will be analyzed as continuous variables and using predefined clinical thresholds to define whether that particular biomarker is elevated. Multivariable logistic regression analyses will be performed using the predictors of the RCRI (i.e. high risk surgery, history of cerebrovascular disease, history of myocardial infarction, congestive heart failure, elevated creatinine and insulin dependent diabetes) as predictors together with the addition of elevation in biomarkers. Discrimination and calibration of the prediction models will be assessed using the c-statistic, Hosmer-Lemeshow test. The net reclassification index (NRI) and the Integrated Discrimination Index (IDI) will be calculated to quantify how well the updated RCRI reclassifies patients as compared to the traditional RCRI.

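### The adjustment set for the primary analysis names no cancer, COPD or ASA class, although all three are collected, so the independent effects of MI, NITE and noncardiac MAPE are at risk of avoidable residual confounding.

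*Combined protocol and SAP*

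**What the plan says.** Section 2.1 sets the objective: "To investigate and compare the independent prognostic effect of the different PMI phenotypes (myocardial infarction and NITE) and noncardiac MAPE on disability". Section 5.1.1 defines the outcome so that "full disability represents a score of 100%, including death".

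Section 7.2 plans multivariable linear regression with an open list of confounders: age, gender, "comorbidities (cardiovascular risk factors), preoperative WHODAS 2.0 score, RCRI and surgical specialty". Section 7.3 carries a similar set into the logistic models for disability free survival. It also lists the RCRI predictors: high risk surgery, cerebrovascular disease, and "history of myocardial infarction, congestive heart failure, elevated creatinine and insulin dependent diabetes".

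Section 5.1.3 lists more baseline data than the models use. ASA class and smoking status are among the demographics, and the current diagnoses read "Currently diagnosed with: diabetes, coronary artery disease, chronic renal failure, cancer, chronic obstructive pulmonary disease, peripheral vascular disease, and hypertension". Neither 7.2 nor 7.3 names cancer, COPD or ASA class as a covariate.

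Section 5.1.2 builds noncardiac MAPE from sepsis, renal failure, unplanned ICU or medium care admission, reoperation and "Respiratory failure including pneumonia and hypoxia or hypercapnia leading to ICU admission for respiratory support".

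**The concern.** An effect is independent only of what the model adjusts for. The named covariates are mainly demographic and cardiac, yet one of the three exposures is noncardiac by definition. Chronic lung disease is a plausible cause of respiratory failure and pneumonia. Cancer is a plausible cause of sepsis, reoperation and ICU admission. Over six months either condition can also produce disability or death without any postoperative event. Section 1 says troponin elevation also accompanies sepsis and respiratory failure, so the same gap can reach NITE.

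Scoring death as 100 makes the outcome sensitive to this. Against the pilot mean of 15 in patients without troponin elevation, each percentage point of excess mortality adds 0.01 × (100 − 15) = 0.85 points to a group mean.

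At stake is whether a coefficient for noncardiac MAPE or NITE reflects the event or partly the disease the patient brought to surgery. The variables are measured, so this part of the confounding can be reduced at the analysis stage.

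**Working it through.** **The plan's own figures.** The plan states no figure for confounding. Its planning contrast is 29 − 15 = 14 WHODAS points for troponin elevation against none (section 4.4). With about 1,000 patients and 20% dropout, about 1,000 × 0.8 = 800 have a 6-month score. The point does not depend on the sample size calculation.

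**Which covariates are covered**

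| Baseline variable | Collected (5.1.3) | In the 7.2 set |
|---|---|---|
| Cardiovascular risk factors | yes | yes |
| Surgical risk | yes | partly, through the high risk surgery item of the RCRI |
| Current cancer | yes | not named |
| COPD | yes | not named |
| ASA class | yes | not named |

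**Size of a possible bias.** For one omitted binary condition in a linear model:

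bias in the MAPE coefficient = (effect of the condition on WHODAS) × (excess prevalence of the condition in patients with MAPE), both given the covariates already in the model.

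Neither input is in the documents. Assume an effect of 5 to 20 points and an excess of 10 to 20 percentage points:

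- Low end: 5 × 0.10 = 0.5 points, and 0.5/14 = 4% of the planning contrast.
- Middle: 10 × 0.10 = 1.0 to 10 × 0.20 = 2.0 points, or 7% to 14%.
- High end: 20 × 0.20 = 4.0 points, or 29%.

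**Against precision.** Assume a residual SD of 20, and use the 19% incidence of any MAPE from section 1 as a stand-in for noncardiac MAPE. The standard error of the MAPE coefficient is then about 20/√(800 × 0.19 × 0.81) = 20/11.1 = 1.8 points. The bias runs from 0.5/1.8 = 0.3 to 4.0/1.8 = 2.2 standard errors.

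**Simulation check.** Inputs were n = 800, 400 runs per setting, residual SD 20, MAPE 19%, condition prevalence 35% and no true MAPE effect. The false-positive rate for MAPE at the nominal 5% level was:

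- condition left out: about 5% to 53%
- condition left out, but a proxy included that correlates 0.3 to 0.6 with it: about 5% to 47%
- condition included: 3% to 8%, nominal within simulation error, with bias within 0.2 points

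For an effect of 10 points and an excess of 20 percentage points, a proxy correlated 0.6 cut the bias from 1.8 to 1.1 points, and one correlated 0.3 cut it from 2.1 to 1.9. Proxies reduce the bias without removing it. The simulation made MI unrelated to the condition, so it says nothing about how far the MI estimate is affected.

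**The case against.** The strongest replies, and what stands of each:

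- **The list is open.** Section 7.2 introduces the covariates as examples, and 7.3 asks only for similar ones. True, so this is not a refusal to adjust for cancer or COPD. But nothing commits the study to them, the bracket narrows what comorbidities means, and covariates chosen after seeing the data would not be prespecified.
- **Existing covariates are proxies.** Age, preoperative WHODAS and surgical specialty carry some of the information, and smoking could count as a cardiovascular risk factor. This stands in part, and the bias must be judged given those covariates. But WHODAS covers only the previous 30 days, and specialty does not separate malignant from benign disease.
- **Surgical risk is already there.** This stands: the RCRI contains a surgical risk item, and specialty is listed as well. Surgical risk is not among the omissions.
- **The model is not written out.** Section 7.2 describes regressions on biomarkers and their combinations, related to phenotypes, without a formula holding separate terms for MI, NITE and noncardiac MAPE. This also stands. The adjustment set still governs whatever model answers the objective.
- **The aim is prognostic.** Section 7.2 itself calls the covariates confounders, and the objective claims independence, so the choice of set matters.

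A reader might go further and infer that MI is better controlled than noncardiac MAPE, and that the comparison therefore tilts toward MAPE. The documents do not support this. It would require cancer and COPD to be less related to MI than to MAPE given the covariates, and nothing in the documents shows that. Cancer may confound MI too, and NITE may share the confounding of the noncardiac events it accompanies.

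**Conclusion.** The point holds as a risk of avoidable residual confounding by measured variables. It does not show that any estimate is confounded, and the direction across the three exposures is unknown.

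The size cannot be derived from the documents. The range of 0.5 to 4 points rests on an assumed effect and an assumed excess prevalence. The low end is negligible; the high end exceeds two standard errors under the assumed SD. The 14-point comparator is an unadjusted pilot contrast for troponin elevation, so it gives scale only and is not a noncardiac MAPE effect.

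The change is worth making because the variables precede surgery, so adjusting for them removes no part of an event's own effect, and because section 5.1.3 already collects them.

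**What to change.** In section 7.2, and in 7.3 for disability free survival:

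1. Prespecify one common adjustment set for MI, NITE and noncardiac MAPE: the covariates already listed plus current cancer, COPD and ASA class. Surgical risk needs no separate term on this account.
2. Confirm that the Toronto cohort records these variables in the same way. Section 4.4 promises only the same inclusion and exclusion criteria, and about half of the pooled data come from there.
3. Report the three estimates with and without the added covariates.

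The cost is a sentence or two in the plan and a few degrees of freedom in a linear model with about 800 scores. At the Utrecht site no new data are needed. The estimated effects may shrink. Confounding will be reduced but not eliminated, because cancer stage is not listed as collected and a yes/no diagnosis does not capture later progression.
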